APPENDIX VI: SURGEON BASELINE SURVEY

You have been given a booklet to complete for this study. The booklet contains some questions related to the role of the patient within the clinical consultation. Your answers will help us to better understand how to support patients in making their decision about breast cancer surgery.

1. Directions on how to complete each set of questions are written on the top of each set.
2. You will be given the site coordinator's name and telephone number. You can call any time with any concerns or questions.
3. It is very important that you return the booklet to us.
4. Please hand the completed survey to the site coordinator.

Thank you for taking the time to help us.

SURGEON BASELINE SURVEY

The following questions focus on the role of the patient within the clinical consultations. You should think about the average breast cancer patient consult in your clinic when answering these questions.

	Strongly Disagree	Moderately Disagree	Slightly Disagree	Slightly Agree	Moderately Agree	Strongly Agree
1. The surgeon is the one who should decide what gets talked about during the consult.						
2. Although health care is less personal these days, this is a small price to pay for medical advances.						
3. The most important part of the standard consult for breast cancer is the physical exam.						
4. It is often best for patients if they do not have a full explanation of their breast cancer.						
5. Patients should rely on their surgeons' knowledge and not try to find out about their breast cancer on their own.						
6. When surgeons ask a lot of questions about a patient's background, they are prying too much into personal matters.						
7. If surgeons are truly good at diagnosis and treatment, the way they relate to patients is not that important.						
8. Many patients continue asking questions even though they are not learning anything new.						
9. Patients should be treated as if they were partners with the surgeon, equal in power and status.						
10. Patients generally want reassurance rather than information about their breast cancer.						
11. If a surgeon's primary tools are being open and warm, the surgeon will not have a lot of success.						

12. When patients disagree with their surgeon, this is a sign that the surgeon does not have the patient's respect and trust.						
13. A surgical plan cannot succeed if it is in conflict with a patient's lifestyle or values.						
14. Most patients want to get in and out of the surgeon's office as quickly as possible.						
15. The patient must always be aware that the surgeon is in charge.						
16. It is not that important to know a patient's culture and background in order to treat their breast cancer.						
17. Humor is a major ingredient in the surgeon's treatment of the patient.						
18. When patients look up information about their breast cancer on their own, this usually confuses more than it helps.						

19. How many years have you been in practice? _____

20. Have you completed a breast or surgical oncology fellowship? Yes or No

21. What percentage of your clinical practice is comprised of breast cancer patients? _____

22. What is your gender? Male or Female

23. Are you of Hispanic, Latino, or Spanish origin? Yes or No

24. How would you describe your racial background?

- American Indian or Alaskan Native
- Asian
- Black or African American
- Native Hawaiian or Other Pacific Islander
- White
- Other: _____

APPENDIX VII: PATIENT ACCESSIBILITY TELEPHONE INTERVIEW GUIDE

Increasing Patients' Engagement in Breast Cancer Surgery Decision Making
ALLIANCE A231701CD

Accessibility Interview Guide

For patients that accepted the decision aid but reported difficulty accessing or using the decision aid website.

This interview guide includes sample questions addressing several constant domains. Within each domain, the interviewer may probe the participant for more in-depth responses or clarification of the response. Throughout the interviews, these domains will remain constant but the EXACT QUESTIONS may be modified based on participant responses

Rave ID: _____

Date of interview: _____

Introduction:

Hello. My name is [Name]. Thank you for taking the time to talk with me today. I'm calling because you agreed to participate in a short interview. Are you still interested in talking?

- *If NO:* Thank you for considering this. Have a great day!

- *If YES:*

Great. Your breast cancer surgeon and clinic team know that you are helping us with this research but they will not be able to hear or see the results of this interview.

The decision for type of surgery is hard for many women diagnosed with breast cancer. The research team is interested in finding ways to help women who need to make this decision. Please let us know if you are uncomfortable or would prefer not to answer a specific question. This isn't a quiz; there are no right or wrong answers. We would just like to hear your thoughts and feelings.

As we discussed when I first talked to you about the interview, we would like to audio-record the interview so that I can focus on our conversation rather than note-taking. Is that still all right with you?

Interviewer Note: If interviewee indicates that it is okay to begin, please start audio recorder. If they say it is not okay, proceed with the interview with expanded note-taking as you are able.

Is it OK if we get started? Please let me know if you have questions or concerns at any time.

QUESTION SET #1: PRESENTATION OF THE DECISION AID TO PATIENTS

Prior to meeting with your surgeon for the first time, you were offered the chance to review a website that had information about breast cancer surgery. We are interested in learning about how the clinic talked about the website with you. You probably would have talked to [Name] about the website.

1. After [Name] described the website to you, were you interested in reviewing the website?

Interviewer Note:

If participant says "I don't remember talking about the website," provide more reminder prompts about it and → proceed to Question 2.

If participant still doesn't remember, → go to QUESTION SET #2: METHOD OF DECISION AID DELIVERY.

2. From what you were told by [Name], in what ways did you think the website would be helpful?
3. If you were to recommend the website to another woman that had been diagnosed with breast cancer, what would you say to her to encourage her to look at the website?

→ Go to QUESTION SET #2: METHOD OF DECISION AID DELIVERY.

QUESTION SET #2: METHOD OF DECISION AID DELIVERY

4. Interviewer Note:

If you do not know how the patient was sent the website, start with 4a.

If you do know, start with 4b.

- 4a. We know that patients who participated in the research study were given and used the website in different ways. Can you tell me about how you were given the website?

PROBE:

- For example, some people had the website link sent to their email. Other people had it sent to a family member's email or accessed the website from a web link on a card. Others just reviewed the website in clinic. How were you given the website?

→ Go to next page.

- 4b. You were sent the website via [email to personal email, other way]. Is that correct?

→ Go to next page.

We are trying to learn the best way to get the website to women who have been diagnosed with breast cancer. In the next few questions, we are looking for your advice about the best way to do this.

If patient received website by EMAIL to PERSONAL email account:

5. What are the advantages of being sent the website through email?

6. What difficulties did you have getting the website by email?

7. Would you have preferred to have been given the website in a different way?

○ *If NO, → proceed to Question #8.*

○ *If YES:*

7a. How would have preferred to receive the website?

7b. Why do you think that would be a better way to be given the website?

→ proceed to Question #8.

8. How could we do a better job in sending out the website?

→ Go to next page.

If patient received website ANOTHER WAY (other than email to their personal account):

9. What are the advantages of getting the website by [insert method of receiving website from interview Question 4a or 4b]?

10. What difficulties did you have getting the website in this way?

11. Why did you chose to get the website this way?

PROBE if they say "I did not chose this method":

- **How would you have preferred to receive the website?**
- **Why would this be a better way to be given the website?**

12. How do you think the process of getting the website could be improved?

→ Go to next page.

Interviewer Note:

If patient did not review the website prior to meeting the surgeon (Question 10 of the baseline survey), → go to QUESTION SET #3: REASONS FOR NOT REVIEWING PRIOR TO SURGEON CONSULT.

If patient did review the website prior to meeting the surgeon (Question 10 of the baseline survey), → go to QUESTION SET #4: PERCEIVED VALUE OF RECEIVING DECISION AID.

QUESTION SET #3: REASONS FOR NOT REVIEWING PRIOR TO SURGEON

13. On one of the surveys that you completed for the research study, you said you did not review the website before meeting with your surgeon. You mentioned, “[insert patient response to Question 10 on baseline survey]”. I’d like to understand that more.

Interviewer Note: Allow patient to make an initial response here.

Interviewer Note: Additional follow-up questions are based on patient’s answer to Question 10 on the baseline survey. → Go to appropriate section below based on the patient’s survey response and ask these questions if they are not covered in the patient’s initial response to Question #13.

- 13a. Survey Response »» “I didn’t have internet access between when I received the website and when I saw my surgeon.”

- 13a.1. How do you usually access the internet?

PROBE:

- Where do you access the internet? For example, some people use a computer at home. Others use a smart phone or go the local library.

- 13a.2. What challenges do you have in accessing the internet?

→ Proceed to Question #14.

- 13b. Survey Response »» “I was feeling too stressed.”

We really want to learn more about this because this is something that many women feel. We know that some women who review the website actually feel less stressed after getting this information from their surgeon. We are trying to learn how to do a better job explaining to women how the website could help them with their feelings of stress.

- 13b.1. Why did you think that the website was something that would not be useful to you?
- 13b.2. Is there something that we could have told you about the website that would have explained how the website could lessen your stress?

→ Proceed to Question #14.

- 13c. Survey Response »» “I didn’t think I needed any information.”

- 13c.1. I’d like to understand more about why you thought you didn’t need any information. Can you tell me more about why you gave this answer?

→ Proceed to Question #14.

- 13d. Survey Response »» “I saw my surgeon very quickly after receiving the website,” “I didn’t receive the email,” or “I couldn’t make the link to the website work,” there are no further questions.

→ Proceed to Question #14.

14. Did you end up reviewing the website after meeting with your surgeon?

If NO, → go to QUESTION SET #5 FINAL QUESTION AND WRAP UP.

If YES:

- **14a. Now that you have had time to review the website, do you think it would have been helpful to review earlier after your diagnosis to help prepare you to meet with your surgeon?**
- **14b. What could we change that would make the information more helpful?**

If nothing could be changed, → go to QUESTION SET #5 FINAL QUESTION AND WRAP UP.

If something could be changed:

14b.1. Looking back, how could [Name] have explained the website differently to better show how it could help you prepare to meet with your surgeon?

→ Go to QUESTION SET #5 FINAL QUESTION AND WRAP UP.

QUESTION SET #4: PERCEIVED VALUE OF RECEIVING DECISION AID

The next few questions are about ways we could potentially improve how we share information with patients about breast cancer surgery.

- 15. How was the information helpful to you in preparing to meet with your surgeon?**
- 16. What could we change that would make the information more helpful?**
- 17. What are your thoughts about the surgery clinic providing you this information before your first visit with the surgeon?**

***Interviewer Note:** The next question relates to the patient's response to Question #11 on the baseline survey.*

If patient answered "No" to Question #11 on baseline survey, → go to QUESTION SET #5: FINAL QUESTIONS AND WRAP UP.

If patient answered "Yes" to Question #11 on baseline survey, ask:

17a. I saw on your survey that you had trouble using the website. Please tell me more about that.

→ *Go to QUESTION SET #5: FINAL QUESTIONS AND WRAP UP.*

QUESTION SET #5: FINAL QUESTIONS AND WRAP UP

We have one final question. I'd like you to think about your own personal experience with being diagnosed with breast cancer and meeting with your surgeon.

- 18. What other things can you think of that would help you prepare to meet with your surgeon for the first time?**

Thank you again for taking the time to talk with me. Is there anything I haven't asked you that you think is important for us to know?

-- END --

Increasing Patients' Engagement in Breast Cancer Surgery Decision Making
ALLIANCE A231701CD

Accessibility Interview Guide

For patients that declined the decision aid.

*****This interview guide includes sample questions addressing several constant domains. Within each domain, the interviewer may probe the participant for more in-depth responses or clarification of the response. Throughout the interviews, these domains will remain constant but the EXACT QUESTIONS may be modified based on participant responses*****

Rave ID: _____

Date of interview: _____

Introduction:

Hello. My name is [Name]. Thank you for taking the time to talk with me today. I'm calling because you agreed to participate in a short interview. Are you still interested in talking?

- ***If NO:*** Thank you for considering this. Have a great day!
- ***If YES:***

Great. Your breast cancer surgeon and clinic team know that you are helping us with this research but they will not be able to hear or see the results of this interview.

The decision for type of surgery is hard for many women diagnosed with breast cancer. The research team is interested in finding ways to help women who need to make this decision. Please let us know if you are uncomfortable or would prefer not to answer any specific question. This isn't a quiz; there are no right or wrong answers. We would just like to hear your thoughts and feelings.

As we discussed when I first talked to you about the interview, we would like to audio-record the interview so that I can focus on our conversation rather than note-taking. Is that still all right with you?

Interviewer Note: If interviewee indicates that it is okay to begin, please start audio recorder. If they say it is not okay, proceed with the interview with expanded note-taking as you are able.

Is it OK if we get started? Please let me know if you have questions or concerns at any time.

QUESTION SET #1: PRESENTATION OF THE DECISION AID TO PATIENTS

Prior to meeting with your surgeon for the first time, you were offered the chance to review a website that had information about breast cancer surgery. We know that you decided you were not interested in reviewing the website at that time.

However, we are interested in learning about how the clinic talked about the website with you. You probably would have talked to [Name] about the website.

1. How did [Name] describe the website to you?

Interviewer Note: If they say "I don't remember talking about the website," provide more reminder prompts about it. If they still don't remember, → go to QUESTION SET #2: REASONS FOR DECLINING THE DECISION AID

2. From what you were told by [Name], in what ways did you think the website would be helpful?

→ Go to QUESTION SET #2: REASONS FOR DECLINING THE DECISION AID

QUESTION SET #2: REASONS FOR DECLINING THE DECISION AID

When the clinic discussed the website with you, you said "[insert reason from decline log]" when you were talking with the clinic staff. I'd like to understand that more.

Interviewer note: Allow patients to make an initial response here.

PROBE based on reason for decline if needed, personalized to their response.

3. We are trying to learn the best way to get the website to women who have been diagnosed with breast cancer. Looking back, how could [Name] have explained the website differently to better show how it could help you prepare to meet with your surgeon?

→ Go to QUESTION SET #3: OPPORTUNITIES TO CHANGE INFORMATION DELIVERY

QUESTION SET #3: OPPORTUNITIES TO CHANGE INFORMATION DELIVER

We are interested in improving how we share information with breast cancer patients to help them prepare to meet with their surgeon.

4. **Would you have preferred to get the information in a different way other than through a website, such as a paper booklet or a DVD?**

If NO: → proceed to Question 6.

If YES:

- 5a. **What way would you prefer? Why do you think that way would be better for you?**

5. **In this research study, patients were offered the website before they met with their surgeon. I know that you were not interested in reviewing the website during this time window. When do you think it would have been a better time for you to be given information about breast cancer surgery?**

→ Go to QUESTION SET #4: FINAL QUESTIONS AND WRAP UP

QUESTION SET #4: FINAL QUESTIONS AND WRAP UP

We have one final question. I'd like you to think about your own personal experience with being diagnosed with breast cancer and meeting with your surgeon.

6. **What other things can you think of that would help you prepare to meet with your surgeon for the first time?**

Thank you again for taking the time to talk with me. Is there anything I haven't asked you that you think is important for us to know?

-- END --

APPENDIX VIII: PATIENT PREPARATORY/INTERACTIONAL IN-PERSON INTERVIEW GUIDE

This interview guide includes sample questions addressing several constant domains. Within each domain, the interviewer may probe the participant for more in-depth responses or clarification of the response. Throughout the interviews, these domains will remain constant but the EXACT QUESTIONS AND WORDING OF THE QUESTIONS may be modified based on participant responses

RAVE ID: _____

Location: _____

Date of completion: _____

Brief introduction:

Thank you for taking the time to talk with me today.

There are different surgical options available for women diagnosed with breast cancer. We are interested in further understanding how you learned about the different options for surgery. We also want to hear about the conversation you had with your surgeon about the different options. By understanding your thoughts and experiences, we hope that we can improve the experience around surgical decision making for women who are diagnosed with breast cancer in the future.

We would like to audio-tape the interview so that I don't have to take as many notes while I'm listening to you. Is that alright with you?

Do you have any questions before we get started?

[question set #1- goal: understand their feelings when coming into the visit, preparatory barriers]

I want to start by having you think back to when you first met with Dr. [surgeon name]. Based on our notes, this would have been on [consult date]. During this visit, you and Dr. [surgeon name] talked about the different surgery options for the breast cancer. Please tell me what your thoughts were about breast surgery before that first visit with Dr. [surgeon name].

What were you expecting would happen during the course of the visit with Dr. [surgeon]?

There is a lot to know about breast cancer and the surgery options. On the first survey you completed when you first met with Dr. [surgeon], we asked about how informed you felt coming into the visit. Please tell me more about how informed you were feeling about those surgery options when you came to clinic to meet with your surgeon for the first time.

I know from reviewing your survey that you said you would prefer to [make the decision yourself/ make the decision after considering surgeons recommendation/make decision with surgery/ have surgery make decision after considering your values/have surgeon make decision].

Women have different responses to that survey question, with some women wanting to be very involved in making the decision for breast cancer surgery and others wanting their surgeon to lead the way. Tell me about why you thought it would be best to [make the decision yourself/ make the decision after considering surgeons recommendation/make decision with surgery/ have surgery make decision after considering your values/have surgeon make decision].

[question set #2: goal- understand what was the conversation, how the surgeon involved them, figure out what was important to the patient (facilitative barriers)]

I know from reviewing the audio-recording of your first visit that Dr. [surgeon name] discussed the different options for surgery with you, things like mastectomy or lumpectomy. Please tell me what you remember talking about with Dr. [surgeon name] regarding these options for surgery.

When Dr. [surgeon name] was describing the options for breast cancer surgery during that first visit, what were your gut feelings about what kind of surgery you wanted to have?

Choose one of the following based on whether surgery received differed from that “gut feeling”

- I know from reviewing your records that you did end up having a [mastectomy/lumpectomy]. Please tell me about the conversation between you and Dr. [surgeon] that led to this decision.
OR
- I know from reviewing your records that your final surgery differed from what you were initially thinking you would want. Please tell me what led to that change.

What, if anything, did Dr. [surgeon] do that made you feel you were part of the planning for your breast surgery?

Probes:

- How well did the surgeon listen to you during the conversation?
- What questions did the surgeon ask you?
- *We will include additional patient-specific probes drawn from their responses on the HCCQ*
- *Climate Questionnaire (follow-up survey)*

Please tell me a little bit about how confident you felt talking with your surgeon during the initial consultation.

Probes:

- What questions did you ask the surgeon during the conversation?
- What did your surgeon do that made you comfortable sharing your thoughts or “gut feelings” about breast cancer surgery?
- Looking back on that conversation, what did you not say then that you now wish you had said to Dr. [surgeon name]? What do you think kept you from saying that during the conversation?
- *Patient-specific additional probes drawn from responses on the HCCQ Climate Questionnaire (follow-up survey)*

When you left that first visit with Dr. [surgeon], did you feel like they understood what was important to you in relation to your breast cancer surgery?

What did the surgeon do that made you feel that way?

Probe:

- How did they show you that they knew what you wanted?
- *Patient-specific additional probes drawn from responses on the HCCQ Climate Questionnaire (follow-up survey)*

Thinking about everything that we talked about, do you feel like you got what you needed from the conversation with Dr. [surgeon]?

If no,

What did you need that you didn't get?

[question set #3- relationship between individual barriers and decision aid based on survey responses]

Before meeting with Dr. [surgeon] for the first time, the surgery clinic shared a website link with you. The website is designed to help women who have been diagnosed with breast cancer and will need to undergo surgery prepare to meet with their surgeon. On your survey, you said that you reviewed the

website before your visit with Dr. [surgeon]. Our next set of questions asks specifically about this website and ways to improve it.

Chose one of the following based on whether the website was helpful or not:

You said on your survey that the website was helpful to you. Please tell us in what ways the website was helpful to you.

How did you use the website to get ready for your visit with Dr. [surgeon]?

OR

You said on your survey that the website was not very helpful to you. Please tell us why you did not find the website to be helpful to you.

How could we make the website better?

The website that you were sent tries to describe the different options for surgery. Some women feel more informed after reviewing the website, whereas others think there is still just so much to know. Tell me a little bit about your thoughts on how the website described the options for surgery.

Probes:

- How was the information helpful?
- In what ways did it fall short?

Additional question if patient responded to Question #1 on the Patient Baseline survey with “I prefer leaving all decisions about my treatment to my doctors”.

Some women want to be more involved in making the decision for breast cancer surgery after reviewing the website. I know that you preferred [leaving all decisions about surgery to your doctors], even after reviewing the website. What changes could we make to the website that might have increased your desire to be more involved in the decision for the type of breast cancer surgery?

If you were talking to a friend who had recently been diagnosed with breast cancer, what would you suggest about how she should use the website?

The website is one resource that we have used to help women who are facing a decision for breast cancer surgery. We are interested in your thoughts about other things that could help these women.

Probes: Ask these based on their response to the earlier questions as a last probe about surgery options

- What things could we have done before you met with your surgeon that would have been helpful for you in getting ready for your visit with Dr. [surgeon]?
- Based on your experiences, what could be done to help women feel more informed?
- What other things could we have done before you met with your surgeon that would have helped you be more involved in making your decision for type of breast cancer surgery?

Final question:

What else should I know about your experience with making the decision for breast cancer surgery?

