This disparity is significant, as it can negatively impact long-term outcomes such as treatment regret, body image, and quality of life.²¹⁻²⁶ The etiology of these disparities is likely multifactorial.^{17,18,27,28} However, patient engagement during the surgical consult is critical for this preference-sensitive choice.⁹⁻¹⁵ Prior studies demonstrate that socioeconomically disadvantaged women have less understanding of treatment options,²⁹⁻³¹ are less likely to recall discussing a choice with their surgeon,^{32,33} and participate less actively in decision making.³⁴ Breast cancer surgery decision aids have already been developed that could address these barriers, making breast cancer surgery an especially appropriate model for our work.

[figure not shown]

Figure 1. Proportion of socioeconomically disadvantaged patients receiving A, BCT and B, reconstruction.

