10.2.1.2 Preparatory/Interactional Barriers

Telephone, video or in-person interviews will be conducted at a private location convenient to the patient. In-person interviews are optimal for this more sensitive topic area; however, telephone or video may be necessary in some circumstances (i.e COVID-19 pandemic). We estimate interviews will occur an average 18 months after the surgeon consult. Although this creates the potential for recall bias, this sequential approach is necessary as the preliminary findings from the quantitative data (primary objectives) are critical for both our sampling strategy and interview content. We will use techniques effective in other studies to minimize recall bias, including prompts from patients own survey responses,⁸⁶ and will preferentially sample patients enrolled later in the study period to minimize time between consult and interview. Prior research demonstrates that breast cancer patients' perceived role in decision making has a lasting impact on quality of life, even >5 years from diagnosis.^{87,88} This data suggests that the decision making process is significant enough that patients – especially those experiencing barriers to engagement—will be able to describe their experience even after delay. We anticipate that 40-50 patients will be needed to achieve informational redundancy,⁸⁹⁻⁹¹ with half the interviews focused on preparatory and half on interactional barriers.

Each interview will begin by asking patients: “Walk me through how you and your surgeon made the decision for type of surgery”. We will specifically probe whether patients perceived that they were able to participate in decision making and express their treatment goals, and whether they felt that the surgeon understood what was important to them. We will then ask open-ended questions that focus specifically on barriers that patients experienced. Using our example of “power imbalance” as a prioritized interactional barrier, a sample question would be, “Tell me how you felt sharing what was important to you with your surgeon.” We will also ask patients, “Based on your experience, what do you think could be done to help patients like yourself?”

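### The default wording of the Appendix VIII interview guide states that surgical options were discussed before the woman gives her own account, and omits the open first question that Section 10.2.1.2 promises

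*Combined protocol and SAP*

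**What the plan says.** Section 10.2.1.2 describes the interviews on preparatory and interactional barriers and fixes how they start: "Each interview will begin by asking patients: “Walk me through how you and your surgeon made the decision for type of surgery". It estimates that they will take place on average 18 months after the consult, and it proposes to limit recall bias with, among other techniques, prompts taken from the patient's own survey answers.

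Appendix VIII is the guide for these interviews. Just before its first question, question set #1 tells the woman: "During this visit, you and Dr. [surgeon name] talked about the different surgery options for the breast cancer". Question set #2 returns to the point: "I know from reviewing the audio-recording of your first visit that Dr. [surgeon name] discussed the different options for surgery with you". The request for her account follows: "Please tell me what you remember talking about with Dr. [surgeon name] regarding these options for surgery".

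The guide describes its own status in two statements: "This interview guide includes sample questions addressing several constant domains", and the "EXACT QUESTIONS AND WORDING OF THE QUESTIONS may be modified based on participant responses".

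Section 1.1 lists lack of awareness of treatment choices among the barriers to engagement. It also reports that socioeconomically disadvantaged women "are less likely to recall discussing a choice with their surgeon".

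**The concern.** The secondary objective is to characterise how persistent barriers limit engagement, so that targets for further interventions can be found. One such barrier is that a woman did not perceive a choice. An interviewer who first says that options were discussed, and then cites a recording as proof, makes that experience harder to report. The woman would have to contradict an apparently documented fact about a visit that took place well over a year earlier. The question that follows asks for memories of the options, so it takes the premise as settled.

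At stake is the qualitative account of this one theme. If it is under-reported, the interviews say less than they should about how it operates, and the inductive coding planned in Section 12.2.1 has less material from which to recognise it.

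**Working it through.** No arithmetic applies, and the plan states no figure on this point. The check sets the passages side by side.

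1. **Opening question.** Section 10.2.1.2 says every interview begins with "Walk me through how you and your surgeon made the decision for type of surgery". Appendix VIII was read from introduction to final question, and this question does not appear. The nearest item asks about the conversation that led to the decision. It comes in question set #2, after both assertions, and in only one of two alternative branches.

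2. **Order of premise and account.** In Appendix VIII the sequence is:
   - an introduction that already refers to a conversation with the surgeon about the options;
   - the first assertion (question set #1);
   - questions on her thoughts, expectations, sense of being informed and preferred role before the visit;
   - the second assertion, citing the recording (question set #2);
   - the first request to describe what was said in the consult;
   - a question on her gut feelings while the surgeon was describing the options.

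   The premise is therefore stated outright twice before she is asked to describe the consult, and the next question presupposes it again.

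3. **Branching.** The guide has alternatives for whether the final surgery matched her first inclination and for whether the website helped, and an extra question for women who preferred to leave decisions to their doctors. It has none for a consult in which options were not discussed.

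4. **Could such a consult occur?** Section 3.2 requires stage 0-III disease and planned breast surgery. It does not require that a woman be a candidate for both operations, and Section 1.1 says only that most are. Such consults are possible, but the documents do not show that any occurred.

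5. **Source of the interviewer's knowledge.** The audio measures in Sections 10.1.4.2, 10.1.5 and 10.1.6 cover patient participation, surgeon facilitative behaviour, whether and when a recommendation was made, and family presence. None records whether more than one option was discussed. The second assertion therefore rests on the interviewer's own review of the recording, with no coded item behind it.

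6. **Does the permitted flexibility cover this?** Wording may change in response to what the participant says. The first assertion precedes any substantive response, so the clause does not clearly reach it.

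7. **Reach.** Sections 10.2.1.2 and 12.2.3 give 40-50 and 50 interviews respectively. The co-primary analyses use surveys and consult recordings, not these interviews, and are untouched.

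**The case against.** The best case on the other side has four parts.

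**The guide is not a verbatim script.** Its items are samples, and Section 10.2.1.2 is the firmer text. If interviewers follow that section, the woman gives a free account before she hears either assertion. This stands in part: a reader might infer from Appendix VIII that every woman will be told options were discussed, but the documents show only that this is the default wording. The two texts still conflict, and an interviewer working from the guide alone would not ask the opening question.

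**Other routes remain open.** The guide asks what, if anything, the surgeon did to make her feel part of the planning, what she left unsaid and why, and what she needed but did not get. It adds patient-specific probes from the Health Care Climate Questionnaire, one item of which rates whether the surgeon offered choices. A low rating can be probed directly. This stands, and it is why a reading that the barrier is suppressed is not supported. These routes come after the premise has been stated, so they reduce the risk without removing it.

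**The interviewees used the decision aid** (Sections 5.1 and 6.1), so ignorance that alternatives exist should be less common among them. That is reasonable. But knowing that options exist differs from perceiving that one's surgeon offered a choice, and Section 1.3 expects some barriers to persist despite the aid.

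**Effect on the target list.** Section 12.2.1 has the quantitative analysis identify and prioritise persistent barriers. It ranks targets by the proportion of patients affected and by perceived impact. A reader might infer that this barrier will be under-represented among the targets; the documents do not establish that.

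**Conclusion.** The concern holds as a risk of leading-question bias together with an inconsistency between Section 10.2.1.2 and Appendix VIII. The inconsistency is a matter of text and needs no assumption. The bias rests on two assumptions: that interviewers use the default wording, and that some interviewees did not perceive a choice. Under them, reports of not perceiving a choice may be too few.

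The size cannot be stated. The documents give no rate of consults without a discussion of options and none of women who perceived no choice, so any count of women affected would be invented. It would also be wrong to derive one from the early-recommendation measure in Section 10.1.4.2, because an early recommendation is compatible with discussing both operations.

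The effect is confined to the qualitative secondary objective and partly mitigated. It is worth correcting because the protocol already contains the better opening question.

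**What to change.** Reconcile Appendix VIII with Section 10.2.1.2 as follows.

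1. Open the guide with the question in Section 10.2.1.2: "Walk me through how you and your surgeon made the decision for type of surgery".
2. Delete the assertion in question set #1 that patient and surgeon talked about the options, and make the matching phrase in the introduction neutral.
3. Replace the assertion in question set #2 with a neutral question such as: *What, if anything, do you remember being said about different options for surgery?*
4. Use any recording-based prompt only after that free account, and only when the interviewer's review of that woman's recording supports it.

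The cost is a rewording of a guide that already allows its wording to change. No patients, visits or data are added. There are two downsides: slightly less cueing of recall at the start of an interview held on average about 18 months after the consult, and a brief check of the recording before the prompt is used. Because no listed audio measure records whether more than one option was discussed, that check is the interviewer's judgement and should be noted in the interview record.
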